In the field of esophageal cancer, gastric cancer and rectal cancer, preoperative neoadjuvant chemotherapy and radiotherapy are more effective than postoperative treatment^[2-4]. On the one hand, preoperative treatment can make the tumor shrink and reduce the probability of tumor cells falling off and incomplete resection during surgery^[3, 5]. A positive surgical margin is strongly associated with local recurrence, which means that the tumor is very aggressive and poorly responsive to systemic therapy. On the other hand, preoperative treatment has the advantage of minimizing surgical procedures and allowing patients to return to normal activities earlier.

In 2012, FOXTROT enrolled 150 patients with T3/4 colon cancer and randomly divided them into two groups: one group received 3 cycles of oxaliplatin and fluorouracil-based chemotherapy before surgery and 9 cycles of chemotherapy after surgery; the other group received direct surgery and completed 12 cycles of chemotherapy after surgery. The results suggested that the rate of tumor regression was more significant in the preoperative chemotherapy group ($p=0.04$) with lower margin positive patients (4% vs. 20%) and higher tumor regression rate (31% vs. 2%)^[6]. The 2019 ASCO abstract reported the updated results of FOXTROT, a total of 1052 patients were enrolled. The incomplete resection rate of patients with preoperative neoadjuvant chemotherapy was reduced. In the neoadjuvant group, the 2-year recurrence rate was improved, although it did not reach statistical significance (14% vs 18%, $P=0.11$). For this reason, the NCCN recommends neoadjuvant therapy (FOLFOX or CAPEOX) for colon cancer patients with T4 or high tumor burden.

NCCN guidelines and CSCO guidelines recommend immunotherapy as the first-line treatment for patients with advanced MSI-H or dMMR colon cancer. The PICC study^[7] published in The Lancet Gastroenterology and Hepatology by [name] revealed that the pCR rate of colon cancer patients with locally advanced MSI-H using immunotherapy reached 76%. Immunotherapy has brought light to the treatment of MSI-H patients. Nowadays, several clinical studies are exploring the neoadjuvant study of immunotherapy combined with chemotherapy for colon cancer.

The combination of antivascular therapy and immunotherapy has shown advantages in liver cancer, kidney cancer and other tumors. Appropriate doses of anti-angiogenic drugs such as apatinib (VEGFR2-TKI) can regulate the tumor immunosuppressive microenvironment and alleviate resistance to anti-PD-1 /PD-L1 therapy^[8].

The purpose of this study is to determine the efficacy and safety of camrelizumab and apatinib combined with chemotherapy (mFOLFOX6) for MSS/pMMR locally advanced colon cancer.

2 Endpoint

2.1 Primary Endpoint

Tumor regression rate of MSS/pMMR patients (Pathological response, percentage of TRG2-4 to all MSS patients, Dworak criteria)

2.2 Secondary Endpoint

The secondary endpoints included the tumor pathological downstage rate, defined as the percentage of patients with a lower postoperative stage than baseline stage, pCR rate, R0 resection rate, 2-year DFS, 2-year EFS and OS for MSS/pMMR colon cancer. The pathological response rate and pCR rate for MSI-H/dMMR patients. Perioperative complication rate, mortality and Adverse events (National Cancer Institute Common Terminology Criteria for Adverse Events [NCI CTCAE], version 5.0).

3.1 Experiment Design

This is a single-institution, single-arm phase II clinical trial. Patients with histopathologically or cytologically confirmed colon adenocarcinoma without distant metastases (T4 or T3 with extramural depth ≥ 5 mm, N₀₋₂, M₀, AJCC 8th) were enrolled.

Patients with microsatellite-stable or proficient mismatch repair (pMMR) received 5 cycles of mFOLFOX6 and camrelizumab (200 mg intravenously on day 1, every 2 weeks) and apatinib (250 mg orally once daily, 2 months). mFOLFOX6 consisted of oxaliplatin 85 mg/m² on day 1, leucovorin 400 mg/m² on day 1, fluorouracil 400 mg/m² bolus on day 1, followed by fluorouracil 2,400 mg/m² continuous infusion over 46 hours, repeated once every 2 weeks. Surgery was scheduled within 4-6 weeks after the last cycle of therapy. 7 cycles of adjuvant camrelizumab plus mFOLFOX6 were administered after surgery.

For patients with microsatellite-instability-high (MSI-H) or deficiency in mismatch repair (dMMR), 5 cycles of camrelizumab (200 mg intravenously on day 1, every 2 weeks) plus apatinib (250 mg orally once daily, 2 months) were given preoperatively and 7 cycles of camrelizumab plus apatinib were given postoperatively.

Tissue samples and peripheral blood samples were collected for further multiomics analysis. The sampling points were: (1) Peripheral blood and colonoscopy tumor tissue at baseline; (2) Peripheral blood before operation; (3) surgical tumor tissue; (4) Peripheral blood 1 month after surgery (5) Peripheral blood after adjuvant chemotherapy

3.2 Sample Size

To determine the sample size, we used the Simon 2 stage optimum design with unilateral alpha 0.05 to achieve the power of 0.8, the pathological response rate (TRG 2-4) is expected to increase from 22.5% to 40%. Considering a 10% shedding rate, it is estimated that 64 patients will need to be enrolled.

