5.3 Primary Study Endpoint

Tumor regression rate of MSS/pMMR patients (Pathological response, percentage of TRG2-4 to all MSS patients, Dworak criteria)

TRG Dworak criteria: Grade 0: no regression; Grade 1: dominant tumor mass with obvious

fibrosis and/or vasculopathy; Grade 2: dominantly fibrotic changes with few tumor cells or groups (easy to find); Grade 3: very few (difficult to find microscopically) tumor cells in fibrotic tissue with or without mucous substance; Grade 4: no tumor cells, only fibrotic mass (total regression or response).

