7.6 Pregnancy

If a female subject becomes pregnant during the study, the subject shall immediately terminate the use of the experimental drug and be discharged from the group; if a male subject's partner becomes pregnant during the clinical study, the subject shall continue the clinical study.

8 End of Treatment

A patient may be discontinued from study treatment at any time if the patient, the investigator, feels that it is not in the patient's best interest to continue on study. If a patient's study treatment must be discontinued, this will not result in automatic withdrawal of the patient from the study.

The following is a list of possible reasons for early discontinuation of study treatment:

Disease progression (patients should be highly encouraged to stay on study treatment until there is confirmed radiographic progression)

Any episode of seizure

Any other adverse event that cannot be adequately managed with dose modifications, including dose interruption for ≥ 28 days may require study drug discontinuation, which must be discussed with the Sponsor.

Protocol violation requiring discontinuation of study treatment

Patient is not compliant with study procedures

Lost to follow-up

Patient withdrawal of consent

9 Protocol Violations

A protocol violation occurs when the patient or Investigator fails to adhere to significant protocol requirements affecting the inclusion, exclusion, patient safety and primary endpoint criteria. Protocol violations for this study include, but are not limited to, the following:

- Failure to meet inclusion/exclusion criteria [no waivers will be granted to meet the eligibility criteria]
- Use of a prohibited concomitant medication
- Dose modifications that are not within the protocol specifications
- Any other deviation that presents significant risk or safety concerns to the patient

Failure to comply with Good Clinical Practice (GCP) guidelines will also result in a protocol violation. The Sponsor, in consultation with the Investigator, will determine if a protocol violation should result in withdrawal of a patient.

10 Statistic Method

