10.1 Analysis Set

Full Analysis Set (FAS) : Patients who met the enrollment criteria and were treated with the study protocol.

Per Protocol Set (PPS) : This analysis set is defined as subjects with no significant protocol deviations during the study or no protocol deviations that have a significant impact on the study results.

Safety Set (SS) : Participants enrolled and receiving at least one cycle of treatment with at least one safety evaluation record constitute the safety set of the study.

The efficacy evaluation of this study will be based on FAS and PPS, in which FAS is the main analysis set. Safety analysis will be based on SS.

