Statistic Analysis Plan

Title of study	Neoadjuvant chemotherapy combined with camrelizumab and apatinib in patients with locally advanced colon cancer: a single-arm, prospective study
NCT number	NCT04625803
Institution	The First Affiliated Hospital, Zhejiang University School of Medicine
major investigators	[name] [name]
Protocol No.	MA-CRC-II-004
Version	1.3
Version Date:	07 November 2021

1.sample size

This was a single-arm study, and no randomization was used. To determine the sample size, we used the Simon 2-stage optimum design with a unilateral alpha of 0.05 to achieve a power of 0.8, and the pathological response rate (TRG 2-4) was expected to increase from 22.5% to 40%. Considering a 10% shedding rate, it was estimated that 64 patients needed to be enrolled.

2. Subject Distribution

Descriptive analysis of subject distribution, including but not limited to enrollment, withdrawal, and major protocol violations. The reasons for screening failure and the reasons for quitting the test were summarized.

3. Demographic and Other Disease Characteristics

Descriptive statistics were performed on sociodemographic characteristics and other disease characteristics. Sociodemographic characteristics include age, sex, etc. Other characteristics include tumor history and past medical history.

4. Analysis of Primary Study Endpoint

The primary endpoint of this study is pathological response rate, which will be aggregated and its 95%CI.

5. Secondary Study Endpoint Analysis

For the temporal event data (DFS, OS) in the secondary endpoints, Kaplan-Meier was used to estimate the median value, estimate the 95%CI of the median DFS/OS, plot a survival curve, and estimate the 2-year disease-free survival and its 95%CI.

Statistical rates and 95%CI were pooled for binary data in secondary endpoints (tumor pathological downphase rate, pCR rate, and R0 removal rate).

6. Safety Analysis

All the statistical analyses were performed using SPSS Statistics 26 (IBM, Armonk, NY, USA). Continuous variables with parametric distributions were evaluated using t tests. Categorical variables were evaluated using the chi-square test (or Fisher's exact test where appropriate). All the statistical tests were two-sided, and the significance threshold for all the P values was 0.05. Graphs were generated using GraphPad Prism (version 10.1.1).

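### Does the undefined 10% shedding allowance leave the trial underpowered once treated but unresected MSS patients stay in the denominator?

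*Protocol*

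**What the plan says.** Protocol section 3.2 names a "Simon 2 stage optimum design with unilateral alpha 0.05 to achieve the power of 0.8" and adds that "the pathological response rate (TRG 2-4) is expected to increase from 22.5% to 40"%. It then inflates for shedding: "Considering a 10% shedding rate, it is estimated that 64 patients will need to be enrolled". SAP section 1 repeats this: "Considering a 10% shedding rate, it was estimated that 64 patients needed to be enrolled". Neither document defines shedding or gives stage sizes or response cut-offs.

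Protocol sections 2.1 and 5.3 give the primary endpoint as "Pathological response, percentage of TRG2-4 to all MSS patients, Dworak criteria". Section 10.1 makes the FAS the main efficacy set and defines it as "Patients who met the enrollment criteria and were treated with the study protocol". A PPS analysis is also planned. Section 5.2 places the pathological assessment after the operation. Section 8 says of stopping study treatment that "this will not result in automatic withdrawal of the patient from the study". The primary analysis (Protocol 10.2.3, SAP section 4) is a rate with a 95% confidence interval.

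**The concern.** Regression grade exists only after surgery, and surgery follows five cycles of treatment and a break of four to six weeks. Some patients may start treatment and never be resected. Dividing 57 by 0.9 is the usual way to allow for patients who contribute no outcome, yet the endpoint and the FAS keep such patients in the denominator. The inflation and the analysis set therefore seem to assume different things.

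In a single-arm comparison with a fixed 22.5%, the denominator affects both error rates. If 40% was meant among resected patients, counting unresected patients as failures lowers the rate that can be reached, and so lowers power. If 22.5% was meant among all treated patients, dropping the unresected makes a positive result easier to obtain. A cut-off derived for 57 patients would also be too lenient if applied to 64.

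**Working it through.** **Inputs.** Null 22.5%, target 40%, one-sided alpha 0.05, power 0.80, shedding 10%, 64 enrolled (Protocol 3.2, SAP 1). The documents give no unresected share, so 2%, 5% and 10% are assumptions. All 64 are assumed to be MSS/pMMR.

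**Formula.** Write a two-stage rule as r1/n1, r/N: stop if stage 1 has r1 or fewer responses, and call the result positive if the total exceeds r. Then

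P(positive | p) = Σ over x from r1+1 to n1 of Bin(x; n1, p) × P(Bin(N − n1, p) > r − x).

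Alpha is this at the null and power is this at the target.

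**Step 1: the plan's own figure.** The exact search for the Simon optimal design gives 5/19, 17/57, with alpha 0.0499 and power 0.804. Then 57/0.9 = 63.3, rounded up to 64. The stated number reproduces. The 57 and the boundaries are reconstructed; the plan does not print them.

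**Step 2: the written denominator.** Both rates refer to all treated MSS patients, and an unresected patient is a non-responder. With 64 in the FAS, 5/19, 19/64 gives alpha 0.0446 and power 0.811. If some patients are lost before treatment, the smallest cut-off that holds alpha at 0.05 (stage 1 at 5/19) is:

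| FAS size | Positive if more than | Alpha | Power at 40% |
|---|---|---|---|
| 57 | 17 | 0.0499 | 0.804 |
| 58–61 | 18 | 0.0343–0.0499 | 0.787–0.811 |
| 62–64 | 19 | 0.0349–0.0446 | 0.797–0.811 |

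Power stays within about 1.3 percentage points of 80% throughout.

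**Step 3: both rates among resected patients, unresected patients kept as failures.** Both rates then shrink alike.

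- 10% unresected: 0.9 × 22.5% = 20.25% and 0.9 × 40% = 36%. Rule 4/19, 18/64: alpha 0.037, power 0.800.
- 5% unresected: 0.95 × 22.5% = 21.4% and 0.95 × 40% = 38%. Rule 5/20, 18/64: alpha 0.050, power 0.805.

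**Step 4: both rates among resected patients, unresected patients left out.** With 57 assessed this is Step 1: alpha 0.0499, power 0.804.

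**Step 5: where the losses come from.** They need the two rates to be on different denominators, or the plan not to be followed.

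- Target among resected patients, null held at 22.5% of all treated, 5/19, 19/64: power 0.786 at 39.2% (2% unresected), 0.744 at 38% (5%), 0.659 at 36% (10%). Part of this is the choice of stage 1. With 5/20, 19/64 (alpha 0.049) the figures are 0.821, 0.780 and 0.696.
- Unresected patients dropped although the null is an all-treated rate, 5/19, 17/57: alpha 0.059 at 22.5%/0.98, 0.075 at 22.5%/0.95, 0.112 at 22.5%/0.90. This contradicts the written denominator.
- The 57-patient cut-off of more than 17 kept as the FAS grows: alpha 0.056 at 58, 0.069 at 60, 0.097 at 64. The plan states no such cut-off.

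**The case for a change.** The best case for acting is that nothing in section 3.2 ties 22.5% and 40% to a denominator. If both came from resected patients and an analyst still tested all treated patients against an unadjusted 22.5%, power would be the 66% to 79% of Step 5. A treated patient without a regression grade is foreseeable, since section 8 lists progression, adverse events and withdrawal of consent as reasons to stop. The FAS wording could also be read as requiring completion of the protocol, surgery included. A rate with a confidence interval is only interpretable once its denominator is fixed.

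It stands that shedding, the missing-grade rule and the boundaries are unwritten. The inference to a power loss does not stand. Section 3.2 gives both rates in one phrase as the same quantity, and sections 2.1 and 5.3 define that quantity over all MSS patients, so different denominators are the least natural reading. Should it nonetheless be true, the error is conservative: with 5/19, 19/64, alpha is 0.016 at a diluted null of 20.25%. The narrower FAS reading sits badly with an endpoint expressed as "percentage of TRG2-4 to all MSS patients", and if both rates were also among resected patients it would return Step 4. A 10% unresected share is itself speculative, because eligibility requires planned surgery and excludes non-resectable disease. The unstated Simon boundaries are a separate matter that does not depend on what shedding means.

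**Conclusion.** No change follows. The enrolment figure reproduces exactly, and none of the stated rules or figures is shown to be wrong. Taken as written, the endpoint and the FAS count a treated MSS patient without a regression grade as a non-responder, which is the usual and conservative choice. On that denominator 64 patients carry about 81% power at alpha 4.5%. The inflation is then at worst unneeded, since 57 would already give 80.4%, and it is natural if shedding means loss before the first dose. Whenever both rates share a denominator, power stays close to 80%.

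This rests on reconstructed boundaries, on all 64 patients being MSS/pMMR (the trial also enrols MSI-H/dMMR patients, and section 3.2 does not separate them), and on 22.5% and 40% being the same kind of rate. What is missing is explanatory detail that the written denominator already settles in practice.

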3.3 Surveillance

Chemotherapy combined with anti-PD-1 antibodies was used every 14 days for 5 cycles, while apatinib treatment was used for 2 months. Chemotherapy, immunotherapy, and apatinib need to be discontinued for 4-6 weeks before surgery. After surgery, 7 cycles of chemotherapy combined with PD-1 antibody were completed. During chemotherapy, patients should be followed up for the quality of life and the toxic and side effects of chemotherapy. Imaging examination should be done to evaluate the tumor size after 5 courses of treatment. Imaging examinations were required before and after postoperative adjuvant chemotherapy.

Imaging reviews were performed every 12 weeks for 1 year after the end of medication and every 6 months after 1 year. Telephone follow-up was conducted every 12 weeks after the end of

treatment, and the total follow-up time was from enrollment to death.

4. Inclusion and Exclusion Criteria:

4.1 Inclusion Criteria:

1. Age \geq 18 years, \leq 75 years
2. Histologically confirmed colon cancer (tumor penetrated of muscularis propria depth \geq 5mm of T3 , T4, N0-2, M0) without distant metastasis (AJCC 8th).
3. ECOG 0-1
4. Surgical treatment is planned after completion of neoadjuvant therapy
5. Patients can swallow pills normally
6. Expected overall survival \geq 12 months
7. Blood routine: no blood transfusion or blood products usage within 14 days, G-CSF or other hematopoietic stimulator was not used. WBC counts $>$ 3000/ μ l, Absolute neutrophil count (ANC) \geq 1500 cells/ μ l, Platelet count \geq 100,000/ μ l, Hemoglobin \geq 9.0 g/dL.
8. AST, ALT and alkaline phosphatase \leq 2.5 times the upper limit of normal (ULN), Serum bilirubin \leq 1.5 x ULN, creatinine $<$ ULN
9. Prothrombin time (PT), international standard ratio (INR) \leq 1.5 \times ULN
10. Patients who have not received systemic chemotherapy or immunotherapy
11. Women of childbearing age must be willing to use adequate contraceptives during the study period of drug treatment;
12. Informed consent has been signed.

4.2 Exclusion Criteria:

1. Patients have received any prior systemic antitumor therapy;
2. Active bleeding within 3 months; Occurrence of arterial/venous thrombosis within 6 months; Hereditary or acquired bleeding (e.g., clotting dysfunction) or thrombotic tendencies; Full dose oral or injectable anticoagulants or thrombolytic drugs for therapeutic purposes are currently being used or have been used recently (10 days prior to the commencement of study treatment); Surgery (except for biopsy) was performed within 4 weeks prior to the study or the surgical incision was not fully healed; Aspirin ($>$ 325 mg/ day) or dipyridamole, ticlopidine, clopidogrel, and silitazone are currently being used or have recently been used (10 days prior to the study).
3. Systemic corticosteroids or other systemic immunosuppressive drugs were used within 2 weeks prior to treatment. Immunosuppressive drugs were started or expected to be used during the trial. Inhaled corticosteroids, physiologic replacement doses of glucocorticoids are allowed.
4. Certain or suspected distant metastases.
5. The patient has a history of autoimmune disease.
6. Serious uncontrolled systemic diseases, such as severe active infections;
7. A person is known to be infected with the immunodeficiency virus (HIV) or known to be HIV-positive;
8. Patients have suffered from other malignancies in the past 5 years except cervical carcinoma in situ or basal cell carcinoma of the skin
9. Untreated chronic hepatitis B or chronic hepatitis B virus (HBV) carriers (HBV DNA $>$ 500

IU/mL) or active HCV carriers with HCV RNA can be detected. Remarks: Inactive hepatitis B surface antigen (HBsAg) carriers, treated and stable hepatitis B patients (HBV DNA < 500 IU/mL) may be enrolled

10. Anti-infective therapy was not discontinued 14 days before the study;
11. A prior history of interstitial lung disease, drug-induced interstitial lung disease, radiation pneumonia, and symptomatic interstitial lung disease or the presence of active pneumonia on a chest CT scan within 4 weeks prior to the study.
12. Patients have a history of intestinal obstruction within six months. Patients with incomplete obstruction syndrome of ileus at the time of initial diagnosis may be enrolled in the study if they have received definitive (surgical) treatment to resolve the symptoms, as assessed by the investigator.
13. Patients have non-resectable factors, including surgical contraindications
14. Patients Have high blood pressure that cannot be well controlled by antihypertensive medication (systolic \geq 140 mmHg or diastolic \geq 90 mmHg)
15. Urine routine indicated urinary protein \geq ++ and confirmed 24-hour urinary protein >1.0g;
16. Known to be allergic to any study drug;
17. Patients have participated in other drug clinical studies within 4 weeks before enrollment;
18. Lactating women
19. According to the judgment of the researcher, the patient may have other factors that may affect the results of the study or cause the study to be terminated, such as alcohol abuse, drug abuse, other serious diseases (including mental diseases) requiring combined treatment. Patients have severe laboratory abnormalities, which will affect the safety of the patient.

5 Clinical Assessments

5.1 Evaluation Method

Full abdominal enhanced CT, chest CT, pathology assessment, tests (blood routine, biochemistry, coagulation function, tumor markers, thyroid function, urine stool routine, electrocardiogram)

5.2 Tumor Assessments

Disease assessments are to be performed as scheduled according to the calendar, regardless of treatment delays resulting from toxicity. Care must be taken in scheduling disease assessments to prevent the introduction of bias based on treatment delays.

Disease assessments will be performed at baseline (Screening) and after 5 courses of treatment. Imaging studies will include a CT scan of the chest, abdomen, and pelvis. Radiographic confirmation of disease progression (appearance of distant metastasis) will be based on RECIST 1.1. Pathological assessment was evaluated after operation.

Imaging examinations were required before and after postoperative adjuvant chemotherapy. Imaging reviews were performed every 12 weeks after the end of all treatments and every six months after 1 year.

